Vital signs: Assessment of vital signs will include measurement of resting blood pressure, pulse, respiratory rate and temperature.

Pregnancy testing: All females of childbearing potential will have a urine pregnancy test at the Screening and Baseline visits.

Survey: We will use the EuroQOL-5D as well as the WPAI: Hepatitis C Quality of Life Surveys. These will be translated into the local language. While these surveys are intended to be self-administered, low literacy rates in our population will require that they be interviewer administered. We will also include brief questions on frequency of drug and alcohol use.

Chart Review: The YRG-JHU ICC maintains an electronic database to monitor client visits, test results and service utilization. Data that are available through this database will be abstracted from these patient records rather than collected de novo. Specifically, we are interested in HIV status and whether participants are engaged in antiretroviral therapy and/or opioid substitution therapy.

b. Study duration and number of study visits required of research participants.

Participants in all Arms will have 4 study visits (Screening, Baseline, End of Treatment and SVR12). Participants in Arm 1 will have an additional 3 visits for interferon injections, and participants in Arm 3 will have an additional two visits to pick up medication refills. The duration of the study will be 16 weeks for Arm 1 and 24 weeks for Arms 2 and 3.

c. Blinding, including justification for blinding or not blinding the trial, if applicable.

This study will not be blinded. In part, this is so that clinicians can appropriately monitor for side effects associated with pegylated interferon alfa-2a. The regimens delivered require different forms of delivery (e.g., pegylated interferon is an injectable medicine) and for different durations of time making blinding not feasible.

d. Justification of why participants will not receive routine care or will have current therapy stopped.

All participants will be able to receive the same routine medical care that they receive at the center and no other therapies will be stopped.

e. Justification for inclusion of a placebo or non-treatment group.

This study does not involve a placebo group.

f. Definition of treatment failure or participant removal criteria.

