Peglyated-interferon alfa-2a is commercially available as Taspiance by Emcure Pharmaceuticals in India and will be provided in this study as 180 µg/0.5 mL pre-filled syringes. Each syringe is to deliver 0.5 mL of drug product. The formulation, which is subcutaneously administered, contains sodium chloride, polysorbate 80, benzyl alcohol, sodium acetate trihydrate, acetic acid, and water for injection. The solution is colorless to light yellow and the pH is 6.0 ± 0.5.

Packaging and Labeling

The PEG will meet all applicable requirements of Good Manufacturing Practices: Manufacture of

investigational medicinal products (July 2003) and the Drug Controller General India (DCGI).

Storage and Handling

Peglyated-interferon alfa-2a prefilled syringes will be stored in the refrigerator at 2 °C to 8 °C (36 °F to 46 °F) protected from light and will not be frozen or shaken. Syringes are for single use only.

b. Justification and safety information if FDA approved drugs will be administered for non-FDA approved indications or if doses or routes of administration or participant populations are changed.

N/A

c. Justification and safety information if non-FDA approved drugs without an IND will be administered.

N/A

7. Study Statistics

a. Primary outcome variable.

The primary outcome will be sustained virologic response (SVR12), which is defined as HCV RNA < lower limit of quantification 12 weeks after treatment completion.

b. Secondary outcome variables.

Adherence for comparison across the three arms will be defined using a combination of the biometric data for Arms 1 and 2 and self-report and pill counts for Arm 3. Serious adverse events requiring dose modification or treatment discontinuation will include primarily laboratory abnormalities including anemia, neutropenia and thrombocytopenia. For any adverse event outcome, we will consider occurrence of any of the side effects commonly associated with treatment with pegylated interferon alfa-2a, including but not limited to fatigue, headache, pyrexia, myalgia, rigors, insomnia, nausea, alopecia, irritability, arthralgia, anorexia, dermatitis, depression, or fatigue.

c. Statistical plan including sample size justification and interim data analysis.

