All analyses will be conducted as intention to treat. We will use a chi-squared test of proportions to compare the proportions that achieve SVR12. Pairwise comparisons with correction for multiple comparisons will be conducted to directly compare Arms 1 and 2, Arms 1 and 3 and Arms 2 and 3. For secondary outcomes, chi squared tests of proportions will be used to compare categorical outcomes and a Wilcoxon rank-sum test will be used to compare adherence.

The primary objective of this study is to test the feasibility of DOT for HCV treatment among HCV-infected persons with substance use history in a resource limited setting. An additional objective is to generate pilot data to plan a larger powered study. We hypothesize that SVR12 will be higher in Arm 1 compared to Arms 2 and 3. Assuming a two-sided $\alpha=0.05$, 50 people in each arm and 70% achieving SVR12 in Arm 3, we will have >80% power to detect a difference of 25% (e.g., 95% completion in the SOF+DAC+PEG).

No interim analyses will be conducted as with 150 participants, it will not be possible to observe statistical differences prior to the completion of the trial.

d. Early stopping rules.

As we do not plan to do interim analyses, the only reason for stopping the trial would be a higher frequency than expected of serious adverse events. We will continually monitor the frequency of serious adverse events and if this frequency is 10% or higher, we will prematurely stop the trial.

8. Risks

a. Medical risks, listing all procedures, their major and minor risks and expected frequency.

It is anticipated that most participants who complete their full course of treatment with optimal adherence will clear hepatitis C from their bodies. However, for those individuals who do not respond to treatment, it is possible that non-response will affect their ability to respond to other drugs for hepatitis C in the future. However, with the newer direct acting antiviral (DAA) regimens, response rates have been demonstrated to be comparable in treatment naïve and prior non-responders. The primary risk related to taking these medications is with respect to side effects associated with pegylated interferon alfa2a.

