It is anticipated that the majority of side effects will be related to pegylated interferon as side effects associated with SOF and DAC are rare. With pegylated interferon, the side effects most commonly reported that are of concern include depression, suicidal thoughts, relapse of drug use by former drug users and bacterial infections complicated or made possible by low white blood cell counts. Notably, previously pegylated interferon has primarily been used as part of 48-week regimens and the majority of the side effects occurred beyond 20-24 weeks of therapy, so we anticipate that the frequency of side effects in our study participants will be lower than what has been observed with longer regimens.

Because we will be delivering daily doses of SOF and DAC for Arm 1 and 2 participants in the field, there are additional risks related to disclosure of a participants' HCV status through the receipt of this medication every day from a field worker.

b. Steps taken to minimize the risks.

Procedures to minimize risk include carefully training personnel 1) to be competent in venipuncture; 2) to recognize and address psychological issues; and 3) to maintain confidentiality. Psychological risks are minimized by the availability of trained counselors in the study clinic. If further assistance is needed, we will have access to the psychiatry department at CIMS. The study clinicians are also trained in CPR as part of medical education in India. Abnormal clinical findings and/or laboratory values will be conveyed in a timely manner to the participants and, with the consent of the subject, form the basis of a facilitated referral to a hospital, clinic, or a physician of the subject's choosing. Subjects who continue to report active drug and alcohol use will be offered individual counseling and referral for treatment of their drug use or alcohol use, should they request one. All participants will receive risk reduction counseling (including the importance of abstaining from alcohol use) at each visit after data collection is completed and prior to scheduling subsequent study visits. This intervention will make our cohort somewhat different from the general population of PWID, but it is useful to provide lower bounds of counseling. We have established cooperation with several drug abuse treatment organizations and this may help facilitate personalized facilitated referrals.

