An AE is any untoward medical occurrence in a clinical investigation subject administered medicinal product and which does not necessarily have a causal relationship with this treatment. An AE can therefore be any unfavorable and unintended sign, symptom or disease temporally associated with the use of a medicinal product, whether or not considered related to the medicinal product.

AEs also include the following:

- Pre- or post-treatment complications that occur as a result of protocol mandated procedure (e.g., venipuncture) during or after screening (before the administration of study investigational medicinal product)
- Any pre-existing condition that increases in severity, or changes in nature during or as a consequence of the study investigational medicinal product phase of a human clinical trial will also be considered an AE.
- Complications and termination of pregnancy
- All AEs that occur from the study screening visit onwards and throughout the duration of the study, including the follow-up off study medication period will be recorded as an AE.

An AE does not include the following

- Medical or surgical procedures (e.g., surgery, endoscopy, tooth extraction, transfusion) performed; the condition that leads to the procedure is an adverse event.
- Pre-existing disease or conditions or laboratory abnormalities present or detected before the screening visit that do not worsen.
- Situations where an untoward medical occurrence has not occurred (e.g., hospitalization for elective surgery, social and/or convenience admissions)
- Overdose without clinical sequelae

- Any medical condition or clinically significant laboratory abnormality with an onset date before the consent form is signed and not related to a protocol-associated procedure is not an AE. It is considered to be pre-existing and should be documented on the medical history form.
- Uncomplicated pregnancy
- An induced elective abortion to terminate a pregnancy without a medical reason

8c1.1. Assessment of Adverse Events

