All AEs will be assessed by the principal investigator or qualified designee (Study Doctor) and recorded on the AE form. The AE entry will indicate whether or not the AE was serious, the start date (AE onset), the stop date (date of AE resolution), whether or not the AE was related to study drug or a study procedure, the action taken with the study drug due to the AE and the severity of the AE. The principal investigator will be responsible for final review and confirmation of accuracy of events, relationship and severity confirmed by signature on the AE form.

The relationship to the study drug will be assessed using a combination of clinical judgement and the following considerations:

- NO: Evidence exists that the adverse event has an etiology other than the study drug. For serious adverse events, an alternative causality will be provided (e.g., pre-existing condition, underlying disease, intercurrent illness or concomitant medication).
- YES: There is a reasonable possibility that the event must have been caused by the investigational medicinal product.

It should be emphasized that ineffective treatment should not be considered as causally related in the context of AE reporting.

The relationship to study procedures (e.g., invasive procedures such as venipuncture or biopsy) should be assessed using the following considerations:

- NO: Evidence exists that the AE has an etiology other than the study procedure.
- YES: The AE occurred as a result of protocol-mandated procedures such as venipuncture.

The severity grading of AEs will be assessed as Grade 1, 2, 3 or 4 using a standard grading scale for severity of adverse events and laboratory abnormalities. This has been adapted from those used for Industry sponsored trials in the US. For AEs associated with laboratory abnormalities, the event should be graded on the basis of the clinical severity in the context of the underlying conditions; this may or may not be in agreement with the grading of the laboratory abnormality.

8c2. Serious Adverse Events

A **serious adverse event (SAE)** is defined as follows:

Any adverse drug experience occurring at any dose that results in any of the following outcomes:

- Death
- Life-threatening situation (subject is at **immediate** risk of death)
- In-patient hospitalization or prolongation of existing hospitalization (excluding those for study therapy or placement of an indwelling catheter, unless associated with other SAEs)

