- Persistent or significant disability/incapacity
- Congenital anomaly/birth defect in the offspring of a subject who received investigational medicinal product
- Other medically significant events that may not be immediately life-threatening or result in death or hospitalization, but based upon appropriate medical and scientific judgement, may jeopardize the subject or may require medical or surgical intervention to prevent one of the outcomes listed above

Examples of such events are as follows:

- Intensive treatment in an emergency room or at home for an allergic bronchospasm
- Blood dyscrasias or convulsions that do not result in hospitalization
- Development of drug dependency or drug abuse

8c2.1. Classification of Serious Adverse Events (SAEs)

- Death is an outcome of an AE, and not an adverse event in itself. In reports of death due to “Disease Progression,” where no other information is provided, the death will be assumed to have resulted from progression of the disease being treated with the study drug.
- The subject may not have been on the study drug at the occurrence of the event. Dosing may have been given as treatment cycles or interrupted temporarily before the onset of the SAE, but may have contributed to the event.
- “Life-threatening” means that the subject was at immediate risk of death from the event as it occurred. This does not include an event that might have led to death if it had occurred with greater severity.
- Complications that occur during hospitalizations are AEs. If a complication prolongs the hospitalization, it is an SAE.
- “In-patient hospitalization” means the subject has been formally admitted to a hospital for medical reasons, for any length of time. This may or may not be overnight. It does not include presentation and care within an emergency department.
- The investigator should attempt to establish a diagnosis of the event on the basis of signs, symptoms and/or other clinical information. In such cases, the diagnosis should be documented as the AE and/or SAE and not the individual signs/symptoms.

A distinction should be drawn between the seriousness and the severity of the AEs. An AE that is assessed as Grade 4 (potentially life-threatening) should not be confused with an SAE. Severity is a category utilized for rating the intensity of an event; and both AEs and SAEs can be assessed as Grade 4. An event is defined as “serious” when it meets one of the predefined outcomes described above.

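### The only SAE outcome in 7b counts an SAE only if it changes or stops dosing, so SAEs after the last dose or without a dose change are not compared between arms as SAEs

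*Combined protocol and SAP*

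**What the plan says.** Secondary objective 2 is safety, tolerability and acceptability in all three arms. Section 7b gives it two safety outcomes. The first is "Serious adverse events requiring dose modification or treatment discontinuation will include primarily laboratory abnormalities including anemia, neutropenia and thrombocytopenia". The second is broader: "For any adverse event outcome, we will consider occurrence of any of the side effects commonly associated with treatment with pegylated interferon alfa-2a", followed by an open-ended list that names depression. Section 7c adds the test: "For secondary outcomes, chi squared tests of proportions will be used to compare categorical outcomes".

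Section 8c is wider. Section 8c2 defines an SAE by its consequence (death, hospitalisation, disability and so on), with no reference to dosing. Section 8c2.1 adds "The subject may not have been on the study drug at the occurrence of the event" and allows that earlier dosing may have contributed. Section 8c1 states that AEs from screening onwards, "including the follow-up off study medication period will be recorded as an AE". The AE form described in 8c1.1 holds seriousness, start and stop dates, relatedness, severity and "the action taken with the study drug due to the AE".

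On timing, treatment lasts 4 weeks in Arm 1 and 12 weeks in Arms 2 and 3, and 4b says "The duration of the study will be 16 weeks for Arm 1 and 24 weeks for Arms 2 and 3".

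**The concern.** The first 7b outcome joins two conditions: the event is serious, and it requires dosing to be modified or stopped. Once dosing is over, the second condition cannot be met. During dosing, an SAE managed with treatment unchanged does not meet it either. Both kinds are SAEs under 8c2 and both will be on file, but no planned comparison treats them as SAEs.

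Section 8a names as the interferon harms of concern "depression, suicidal thoughts, relapse of drug use by former drug users and bacterial infections". A hospitalisation for one of these in Weeks 5 to 16 of Arm 1 would count in the any-AE proportion exactly as a headache would. At stake is whether the trial's safety comparison can show a difference in serious harm between a 4-week interferon regimen and a 12-week oral one.

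Tolerability has a related gap. Stopping a drug because of an AE is its most direct measure, and no outcome counts it regardless of seriousness.

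**Working it through.** **1. Reproduce the stated durations.** Treatment plus 12 weeks: Arm 1, 4 + 12 = 16 weeks; Arms 2 and 3, 12 + 12 = 24 weeks. Both agree with 4b. The Table 3 footnotes instead put Arm 1's end-of-treatment and SVR12 visits at Weeks 5 and 17. These timings need reconciling, but the conclusion does not change.

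**2. Share of follow-up in which an SAE can count.**
- Arm 1: 4/16 = 25% countable, 12/16 = 75% not.
- Arms 2 and 3: 12/24 = 50% countable, 50% not.
- Ratio of countable windows: 12/4 = 3.
- With the Table 3 timing, the uncountable share in Arm 1 is 12/17 = 71% from the end-of-treatment visit, or 13/17 = 76% from Week 4.

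Extended or restarted courses (4a5.2) would lengthen the countable window for those participants.

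**3. What can trigger the outcome.** The dose-reduction text and Tables 1 and 2 in 4a5.2 describe dose modification only for interferon, hence only for Arm 1. In Arms 2 and 3 the outcome can arise only through discontinuation. This raises Arm 1's count relative to the others, while the shorter window lowers it.

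**4. Size under assumed rates.** The documents give no SAE rate. Assume a constant weekly rate r. Expected participants with an SAE per 50 = 50 × (1 − exp(−r × weeks)). The countable figures are upper limits, because they assume that every on-treatment SAE changes dosing.

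| Weekly rate | Arm 1: all, 16 wk | Arm 1: countable, 4 wk | Arms 2 and 3: all, 24 wk | Arms 2 and 3: countable, 12 wk |
|---|---|---|---|---|
| 0.25% | 2.0 | 0.5 | 2.9 | 1.5 |
| 0.5% | 3.8 | 1.0 | 5.7 | 2.9 |
| 1% | 7.4 | 2.0 | 10.7 | 5.7 |

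**5. Direction.** Fix Arm 2 at 0.25% per week, so its countable expectation is 50 × (1 − exp(−0.0025 × 12)) = 1.48. Vary Arm 1:
- Rate ratio 1: 50 × (1 − exp(−0.0025 × 4)) = 0.50 v 1.48.
- Rate ratio 2: 50 × (1 − exp(−0.005 × 4)) = 0.99 v 1.48. Arm 1 looks safer despite a doubled rate.
- Rate ratio 3: 50 × (1 − exp(−0.0075 × 4)) = 1.48 v 1.48, a tie.
- Rate ratio 4: 50 × (1 − exp(−0.01 × 4)) = 1.96 v 1.48. Arm 1 looks worse.
- Rate ratio 2, but only half of Arm 2's on-treatment SAEs lead to a stop: 0.99 v 50 × (1 − exp(−0.00125 × 12)) = 0.74. Arm 1 looks worse.

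The sign is therefore not fixed by the windows.

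**6. Which window the remedy needs.** Take 0.5% per week in Arm 1 and 0.25% in Arm 2, with independent binomial counts and 50 per arm.

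| SAEs counted | Arm 1 v Arm 2, per 50 | P(Arm 1 count higher) |
|---|---|---|
| 7b as written (4 v 12 wk) | 0.99 v 1.48 | 25% |
| All, to end of follow-up (16 v 24 wk) | 3.84 v 2.91 | 57% |
| All, to Week 16 in both | 3.84 v 1.96 | 72% |

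With equal rates of 0.25%, end of follow-up still gives 1.96 v 2.91 (ratio 0.67), while the common Week 16 window gives 1.96 v 1.96. Removing the dose-change condition is necessary but not sufficient; the window must also be common.

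**The case against.** The strongest reply is that nothing is lost. AEs are recorded through off-drug follow-up, SAEs go to the IRBs within 24 hours, and 7d monitors SAE frequency against 10%. The any-AE outcome is open-ended and names depression, so a late hospitalisation does enter an arm comparison. This is right as far as it goes. A reader might infer that late SAEs appear in no arm comparison at all, and the documents do not support that. What remains is that the any-AE proportion does not separate serious from mild, and the 7d rule names no arm.

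Second, 8c governs recording and 7b governs outcomes, so a narrower outcome is a permissible choice, and the 7b sentence is partly descriptive. That is fair: the two sections do not contradict each other. But the sentence stands under the secondary outcome variables, and no wider SAE outcome is named elsewhere.

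Third, a reader might infer that the shorter window must make the interferon arm look safer. It need not, as step 5 shows. The inference relies on constant rates, on a rate ratio below 3, and on every on-treatment SAE changing dosing in all arms.

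Fourth, a reader might infer that every stop for an event that is not serious under 8c2 is left out. Tables 1 and 2 apply the word serious to dose-modification triggers, including laboratory thresholds and even mild depression with no dose change. On that usage some such stops may already count. This makes the outcome ambiguous; it does not supply a measure of discontinuation due to any AE.

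Last, this is a pilot with 50 per arm. Rounded counts of 1 v 2 or 4 v 2 are far from significance (Fisher p = 1.0 and 0.68). That stands, and it limits the point to a fair description of harm rather than a test result.

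**Conclusion.** The point holds as a defect in how a secondary safety outcome is defined. Read literally, the SAE outcome covers at most 25% of Arm 1's follow-up and 50% of that in Arms 2 and 3, over windows that differ threefold, with dose modification as a trigger described in one arm only. These statements rest on the documents' own schedule and wording. SAEs outside those limits are compared only within the any-AE proportion, and discontinuation due to any AE is not an outcome.

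The event counts and probabilities rest on assumed constant weekly rates and are illustrations. The net direction of bias is unknown. The 72% figure belongs to a common Week 16 cut-off; counting to the end of each arm's follow-up gives 57% on the same rates. The primary outcome and the reporting of SAEs are unaffected. The change is worth making because the interferon arm's safety is a stated objective and the data will already exist.

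**What to change.** In 7b, replace the SAE outcome with two outcomes compared by arm:
- (a) Any SAE as defined in 8c2, whether or not dosing changed, from first dose over a common window, for example to Week 16 in all arms. Also tabulate all SAEs to end of follow-up with person-time.
- (b) Permanent discontinuation of any study drug because of an AE of any seriousness, taken from the action-taken entry on the AE form. State beside it that the arms have 4 and 12 weeks of treatment in which a stop can occur.

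Keep the SAE with dose change as a descriptive subset. Reconcile the use of serious across 7b, Tables 1 and 2, and 8c2, and reconcile the Arm 1 visit weeks in Table 3 with 4b, since a Week 16 cut depends on them. The procedures listed for the 12-week post-treatment visit in 4a5.5 do not include an AE assessment; aligning that list with 8c1 would secure the off-drug data.

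The cost is wording and a table, because seriousness, dates and action taken are already on the form. The downside is that two outcomes replace one, with few events expected at 50 per arm, so the result should be read as description.
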